6.2 RSV Surveillance: Active and Passive

6.2.1 Active and Passive Components of Surveillance

RSV surveillance will comprise both active and passive components. All queries for RSV-suspect illnesses will be made using an IRB/IEC-approved script, if applicable.

- Active Surveillance (applicable to all subjects through the D+180 visit):
 - Study staff will contact the maternal subject and a parent/guardian of the infant subject via telephone call or SMS on a once weekly interval through the D+180 visit to query for an RSV-suspect illness. Newly-discovered RSV-suspect illnesses as assessed by the presence of “trigger symptoms” (see Section [6.2.2](#) and Table 2) will precipitate a home or clinic visit for evaluation (see Section [6.2.3](#)).
 - Study staff will re-evaluate (at home or in the clinic) all *infant* subjects with RSV-suspect illnesses between 2 and 3 days after any initial RSV surveillance visit to ascertain worsening in the illness. This re-evaluation will include the same procedures outlined in Section [6.2.3](#).
- Passive Surveillance (applicable at any time during the study):
 - If the maternal subject develops any symptom suggestive of an RSV-suspect illness, or shows signs of worsening of a previously-evaluated RSV-suspect illness, she should contact the study site directly within 3 days of the onset/worsening of symptoms.
 - If an infant develops symptoms of an RSV-suspect illness while on study, or shows signs of worsening of a previously-evaluated RSV-suspect illness, parents or guardians should contact study staff directly within 3 days of the onset/worsening of symptoms.
 - Any newly-discovered RSV-suspect illnesses as assessed by the presence of “trigger symptoms” (see Section [6.2.2](#) and Table 2) will precipitate a home or clinic visit for evaluation (see Section [6.2.3](#)).

- Study staff will re-evaluate (at home or in the clinic) all *infant* subjects with RSV-suspect illnesses between 2 and 3 days after any initial RSV surveillance visit to ascertain worsening in the illness. This re-evaluation will include the same procedures outlined in Section 6.2.3.

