16.6. Missing, Unused, and Spurious Data

In general, there will be no substitutions made to accommodate missing data points. All data recorded on the eCRF will be included in data listings that will accompany the CSR.

For maternal subjects, if delivery date is missing, it will be imputed as the estimated delivery date (EDD) to establish the projected end time for their efficacy analysis.

When tabulating AE data, partial dates of AE onset will be handled as follows:

- If the day of the month is missing, the onset date will be assumed to be the date of either the first, in order to conservatively report the event as vaccine-emergent, unless the month reported clearly indicates the event would be outside the window for vaccine-emergent events, in which case no date will be imputed.
- If the onset day and month are both missing, the event onset will be coded to the day of vaccination (the birth date for infant subjects) in order to conservatively report the event as vaccine-emergent, unless it is clear by reference to the year that the event is outside the window for vaccine-emergent events.
- A completely missing onset date will be coded as the day of vaccination.

A conservative approach will be taken to assess the relationship of an AE to vaccine: if the relationship of an event is missing, it will be considered treatment-related. Missing severity for an AE will not be imputed.

When determining whether the concomitant medication was taken post-vaccination (i.e., start date is on or after the vaccination date), missing or incomplete start date will be handled as follows:

- If the start date is completely missing and the reason for use is not marked as preexisting, it will be treated as post-vaccination.
- If only the year is provided and the year is on or after the year of the vaccination and the reason for use is not marked as preexisting it will be treated as post-vaccination.
- If only the year and month are provided and the year and month are on or after the year and month of the vaccination and the reason for use is not marked as preexisting it will be treated as post-vaccination.

When tabulating concomitant medications data associated with the RSV surveillance illnesses, partial or missing dates of start and stop will be handled as follows:

- If a start date is completely missing, it will be assigned as Day 14 (start of the RSV surveillance for each subject) for maternal subjects (the birth date for infant subjects).

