- If a stop date is missing, it will be assigned Day 180 post-delivery (end of the RSV surveillance for all subjects).
- If the day and month are missing for a start date, it will be assigned 01 January of the year or Day 14 for maternal subjects (the birth date for infant subjects) whichever is the latest.
- If the day and month are missing for a stop date, it will be assigned Day 180 post-delivery (end of the RSV surveillance for all subjects) or December 31 of the year whichever is the earliest.

- If the day is missing for a start date, it will be assigned the 1st day of the month or Day 14 (start of the RSV surveillance for each subject) for maternal subjects (the birth date for infant subjects) whichever the latest.
- If the day is missing for a stop date, it will be assigned the last day of the month or Day 180 post-delivery (end of the RSV surveillance for all subjects), 01 May for 2016 or December 31 of the year whichever is the earliest.

When determining preterm birth categories (Very preterm and Moderate to late preterm), if the study EDD is missing other available data (e.g. LMP or third trimester ultrasound, or GA at birth reported on the SAE narrative) will be used to determine the GA at birth.

When tabulating RSV surveillance illness episodes, onset or end date will be determined as follows:

- Parent-reported illness start date and return to normal date will be used as the start/end date for an episode.
- In the case of a missing or incomplete start date or return to normal date:
 - If start date is missing: impute the start date by the first contact date when parent reported symptoms or the first on-site visit date when site observed symptoms (whichever is earlier).
 - If return to normal date is missing: impute the return to normal date by the last contact date when parent reported symptoms or the last on-site visit date when site observed symptoms (whichever is later).
- If there is a “2~3 days after initial” visit record after the episode end date AND the record indicates site-observed symptom(s), adjust the episode end date to coincide with on-site visit date (episode will be extended).
- Each hospital stay is considered a single illness episode.

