- If a parent-reported outpatient illness episode overlaps with a hospital stay, or extends to the onset of a hospital stay, or begins at the end of a hospital stay, then the episodes will be merged using the earliest of episode start or hospital admission as the start date and the latest of the hospital discharge or parent-reported episode end date as the end date.
- If 2 illness episodes occur within 7 days (≤ 6 days), combine them to form a single illness episode (two episodes will be combined into one).
- Additional imputations may be performed by a Novavax medical staff if warranted in a blinded fashion.

When respiratory hospitalization admission and discharge dates for an infant subject are missing (or incomplete), they will be determined as follows:

- If the day of the month is missing:
 - The admission date will be imputed as the 1st of the month or the start date of the corresponding SAE whichever is later.
 - The discharge date will be imputed as the last of the month or the end date of the corresponding SAE whichever is earlier.
- If both the day of the month and the month are missing:
 - The admission date will be imputed as the 1st of January or the start date of the corresponding SAE whichever is later.
 - The discharge date will be imputed as the 31st of December or the end date of the corresponding SAE whichever is earlier.
- If the year is missing, the admission date or the discharge date will be imputed as the onset or the end date of the corresponding SAE, respectively.

Meeting all of the following conditions will be required to link a RSV surveillance illness episode and a concomitant medication:

- Answer to “Did subject take any medications/treatments for these symptoms?” on the RSV Surveillance CRF is marked as “Yes”.
- The reason for taking the medication is marked as “Respiratory Surveillance” or “Unsolicited Adverse Event”. If it is marked “Unsolicited Adverse Event”, a manual review of the reported medications by clinician to confirm the link.
- Medication start date is not later than the illness end date.
- Medication stop date is on or after the illness onset date.

The following data conventions will be used for handling serology samples with respect to collection windows and missing or incomplete collection dates.

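### SAP 16.6: a 01 May 2016 term in the day-missing stop-date rule misdates RSV-illness medications stopped in May to December 2016 and breaks their illness link; separately, the maternal Day 14 start floor does not match surveillance from vaccination

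*SAP*

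**What the plan says.** SAP 16.6 has a set of date rules for concomitant medications associated with RSV-surveillance illnesses. They cover incomplete dates only: "partial or missing dates of start and stop will be handled as follows". There are three stop-date rules.

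- Fully missing: "If a stop date is missing, it will be assigned Day 180 post-delivery (end of the RSV surveillance for all subjects".
- Day and month missing: "If the day and month are missing for a stop date, it will be assigned Day 180 post-delivery" or 31 December of the year, whichever comes first.
- Day missing: "If the day is missing for a stop date, it will be assigned the last day of the month or Day 180 post-delivery", with two further candidates, "01 May for 2016 or December 31 of the year whichever is the earliest".

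Only the third rule contains the 01 May 2016 date. For a fully missing maternal start, "it will be assigned as Day 14 (start of the RSV surveillance for each subject) for maternal subjects"; the two partial-start rules for mothers use Day 14 as a floor. Infants use the birth date instead.

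Later in the same section, a medication is linked to an illness episode only if every listed condition holds. One is that the medication starts no later than the illness ends. Another is "Medication stop date is on or after the illness onset date".

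Protocol 6.2.1 describes surveillance by subject time: "Active Surveillance (applicable to all subjects through the D+180 visit". The maternal endpoint in SAP 4.2.3 counts RSV illness from vaccination, and Protocol 6.1.1.4 has staff ask mothers about RSV symptoms at the Day 7 visit.

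**The concern.** A fixed calendar date sits in a rule that otherwise works on month-end and each subject's own Day 180. Because the rule takes the earliest candidate, that date overrides the recorded month whenever the month is May 2016 or later in that year. The result can be a stop before the recorded month, before the recorded start, or, for an infant born after 01 May 2016, before birth. Such a stop then fails the link condition for any illness that began after 01 May 2016, and the treatment is lost from the tabulation of medications by illness.

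The rules also become inconsistent with each other. A 2016 stop known only to the year goes to the earlier of Day 180 and 31 December, which is possible. A stop known to be in July 2016 goes to 01 May, which is not. More information gives a worse date.

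The Day 14 start floor is a second, unrelated inconsistency. It can place a mother's medication start after an illness that ended in the first two weeks.

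**Working it through.** The plan gives no figure to reproduce here, so the check applies the SAP 16.6 rules as date logic.

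**Rules**

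- Stop, day missing = min(month-end, Day 180, 01 May 2016 if the year is 2016, 31 December). The 31 December candidate can never bind, because month-end is never later.
- Maternal start, day missing = max(first of month, Day 14).
- Link requires stop ≥ illness onset and start ≤ illness end.

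**Step 1: imputed stops.** Assume Day 180 does not bind (01 June 2017 for the 2016 rows, 01 December 2017 for the last row).

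| Recorded stop | SAP rule | 01 May term deleted |
|---|---|---|
| January 2016 | 31 Jan 2016 | 31 Jan 2016 |
| April 2016 | 30 Apr 2016 | 30 Apr 2016 |
| May 2016 | 01 May 2016 | 31 May 2016 |
| July 2016 | 01 May 2016 | 31 Jul 2016 |
| December 2016 | 01 May 2016 | 31 Dec 2016 |
| July 2017 | 31 Jul 2017 | 31 Jul 2017 |

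June and August to November 2016 behave like July. The term changes May to December 2016 only.

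**Step 2: the link.** Take each onset date in 2016, with the medication stopping in the onset month, day unknown. The stop condition fails for every onset from 02 May to 31 December: 30 + 30 + 31 + 31 + 30 + 31 + 30 + 31 = 244 of 366 dates. With the term deleted, 0 of 366 fail.

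**Step 3: one case.** Infant born 01 May 2016, so Day 180 is 28 October 2016. Illness onset is 10 July 2016 and the stop is recorded as July 2016.

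- SAP rule: min(31 Jul, 28 Oct, 01 May, 31 Dec) = 01 May 2016, 70 days before onset. The link fails.
- If only the year were known: min(28 Oct, 31 Dec) = 28 October 2016. The stop condition holds.

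**Step 4: Day 14 floor.** Vaccination 01 March 2017, so Day 14 is 15 March. The illness ends on Day 10 (11 March), and the start is recorded as March 2017. The imputed start is max(01 Mar, 15 Mar) = 15 March, after 11 March, so the link fails.

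As a contrast, take vaccination on 01 May 2016, illness from 05 to 15 July 2016 and start recorded as July 2016. The imputed start is max(01 Jul, 15 May) = 01 July, so the start condition holds. The floor therefore plays no part in the May to December 2016 failures.

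**Step 5: rough scale.** SAP Appendix 1, section 6.1, assumes accruals of 20, 154 and 210 in the first three hemispheric seasons. Their sum is 384, or 384/4,600 = 8.3% of mothers. These are simulation inputs, not observed enrollment. They agree with SAP Table 1: if n mothers were randomized 1:1 and the rest 2:1, then n/2 + (4,600 − n)/3 = 1,562 gives n = 172, against 20 + 154 = 174.

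**The case against.** The strongest defense is that this hardly matters, and much of it stands. The primary and secondary endpoint definitions (SAP 4.2.1 and 4.2.2) make no use of the medication link. The general medication summary in SAP 8.2 counts anyone with a recorded medication, including those with partial start dates, and SAP 16.6 keeps all recorded data in listings. The rule is the same in both arms. If the first three accrual seasons are the ones in follow-up during 2016, few mothers and infants are exposed to it, and only their day-missing stops count.

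Some discretion is built in, but it does not rescue the rule. The allowance for extra blinded imputations by medical staff is in the list for illness-episode dates, not medication dates. Clinician review in the link rule applies to medications marked as given for an unsolicited adverse event, and it is an added requirement rather than an override of the date conditions. Reading the 01 May and 31 December terms as a single year-end term, with 01 May serving for 2016, gives the same dates. If the date was once a data cut-off, it has no place in a plan for the final dataset.

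A reader might infer more than the documents support:

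- That all 2016 stops are capped. Complete dates are not imputed, year-only and fully missing stops carry no such term, and January to April stops are unchanged.
- That any illness after May 2016 loses its partially dated treatments. The cap follows the stop year: onset 28 December 2016 with a stop recorded as January 2017 gives 31 January 2017 (if Day 180 is later), and the condition holds.
- That the imputed stop always precedes the start. A medication begun in April 2016 and stopped in July 2016 gets 01 May, after its start.
- That a whole Southern season is lost. The documents give no enrollment calendar, and Protocol 1.2.3 puts the South African peak in February to July, partly before May.

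On Day 14, the SAP states its label openly, so this is a definition to reconcile, not a calculation error.

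**Conclusion.** The concern holds in a narrow form. The day-missing stop rule gives a wrong date for every RSV-illness medication recorded as stopping in May to December 2016 without a day, except where Day 180 falls on or before 01 May 2016 and sets the date in any case. For June to December the imputed stop precedes the recorded month. When onset is after 01 May 2016, the SAP's own link condition then fails. The term conflicts with Day 180 as the end of surveillance and with both neighboring stop rules, and the documents give no reason for it.

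The 244 of 366 figure assumes that stop and onset fall in the same month and that Day 180 does not bind. It describes the rule's reach over calendar dates; it is not a proportion of records. The number of partial dates is not stated and cannot be derived. The 8% exposure figure is an assumption about which seasons were in follow-up during 2016.

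The Day 14 floor is a separate mismatch with surveillance from vaccination. It matters only for missing or partial maternal starts in illnesses that ended before Day 14.

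Both are housekeeping corrections to the illness-linked medication tabulation. Nothing here touches an efficacy conclusion.

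**What to change.** 1. Delete the 01 May 2016 term, so that a day-missing stop becomes the earlier of month-end and Day 180 post-delivery. The 31 December candidate can go too, since it never binds.
2. Add that an imputed stop may not precede the recorded start. This is still needed after step 1, because Day 180 can fall before the start of a treatment for an illness that runs past the D+180 visit.
3. In the three maternal start rules, replace Day 14 with the day of vaccination, to match SAP 4.2.3 and the Day 7 symptom query.

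The cost is a few words in SAP 16.6, a small change to the date program, and a rerun of the illness-linked medication tabulation if it has already been produced. No new data are needed, and the efficacy analyses do not change.

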6.2.4 Follow-up of RSV-Suspect Illnesses

Following the evaluation of an RSV-suspect illness outlined in Section 6.2.3, the clinical site will:

- For *symptomatic infant* subjects, schedule a follow-up visit in 2 to 3 days to ascertain whether the illness is worsening.
 - The follow-up visit will include the same procedures outlined in 6.2.3.
 - Parents/guardians will be strongly encouraged to report any worsening after the follow-up visit, including hospitalizations, which may trigger any number of additional follow-up visits at the investigator's discretion.
 - In the event that an infant is hospitalized, site staff are encouraged to perform a follow-up visit in-hospital, if permissible under local administrative and ethical review procedures.
- For *symptomatic maternal* subjects, and for *symptomatic infant* subjects after the first follow-up visit described above, a weekly contact by telephone/SMS will be performed to ascertain respiratory symptom status through to the D+180 visit, and to monitor the

status of RSV-suspect illnesses until symptoms have resolved, or have returned to baseline if after the D+180 visit.

- In the event new and/or worsening symptoms are reported during active or passive follow-up, an in-clinic or home RSV-surveillance visit may be scheduled at the investigator's discretion for an evaluation to occur as soon as possible, and a re-evaluation as per Section 6.2.3 may be performed.
 - At the investigator's discretion, collection of ONE more respiratory specimen for pathogen detection for infant subjects who have developed qualitatively different or quantitatively worse symptoms. *Note that no more than 3 respiratory specimens should be collected from an infant within the same episode.*
 - If the new or worsening symptom in the maternal subject is associated with a respiratory episode for which a specimen has already been obtained, the investigator may exercise his/her judgement as to the utility of an additional swab.

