4.2. Study Endpoints

4.2.1. Primary Efficacy Endpoint (In Infant Subjects)

- Percentages of infants with medically-significant RSV LRTI from delivery through 90, 120, 150, and 180 days of life, as defined by:
 - The presence of RSV infection confirmed by detection of the RSV genome by RT-PCR on respiratory secretions (obtained within the continuous illness episode which fulfills the other criteria listed below); AND
 - At least one manifestation of lower respiratory tract infection (LRTI) from among the following: cough, nasal flaring, lower chest wall indrawing, subcostal retractions, stridor, rales, rhonchi, wheezing, crackles/crepitations, or observed apnea; AND
 - Evidence of medical significance as defined by the presence of:
 - EITHER hypoxemia (peripheral oxygen saturation [SpO_2] < 95% at sea level or < 92% at altitudes > 1800 meters) OR
 - Tachypnea (\geq 70 breaths per minute [bpm] in infants 0 to 59 days of age and \geq 60 bpm in infants \geq 60 days of age).

Data elements supporting the three (3) criteria for a primary endpoint case will be present within the start and stop dates of a continuous illness episode and derived from clinical observations (LRTI signs and symptoms and respiratory rates) made by qualified clinical trial site staff, pulse oximetry performed by site personnel using a Masimo RAD-5 pulse oximeter supplied by the sponsor, and RSV detection based on study-specified RT-PCR performed by the validated GenMark eSensor assay in place at the central laboratory (Marshfield Clinic Research Institute, Marshfield, Wisconsin).

A Clinical Endpoint Adjudication Committee (CEAC) composed of expert pediatricians (see Section 10.2) will carry out a blinded review of all potential primary endpoint cases to determine if they fulfill the primary endpoint criteria in a temporally plausible relationship consistent with RSV disease as observed in clinical practice. Only CEAC-confirmed cases will be used for the primary endpoint.

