16.7. Data Handling for Incidence Calculations

- Any infant with an RSV illness fulfilling the primary, secondary, or an exploratory efficacy endpoint will be counted once in the incidence analysis using the first episode even if this endpoint has been recorded multiple times and in several days.
- Any infant with an RSV illness fulfilling the primary, secondary, or an exploratory efficacy endpoint who dies before 90 days of age will be counted as having reached the endpoint and will be included in all subsequent analyses of 0-120, 0-150, and 0-180 days of age.
- Any infant who dies for of any illness other than an RSV LRTI will be included in the non-infected group for analysis.
- Two consecutive illness episodes that are within 7 days of each other will be combined as one continuous episode for the efficacy analysis.

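### With a recorded return-to-normal date, only a 2–3 day follow-up visit extends an illness episode; qualifying findings at other outpatient visits after that date count only by follow-up, merging or unspecified imputation

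*SAP*

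**What the plan says.** SAP 16.6 sets the default for episode dates: "Parent-reported illness start date and return to normal date will be used as the start/end date for an episode". It then gives two rules through which staff observations can affect the end date.

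- **Return date missing.** The SAP says to "impute the return to normal date by the last contact date when parent reported symptoms or the last on-site visit date when site observed symptoms". The later of the two dates is taken, and any type of on-site visit qualifies.
- **Return date recorded.** The rule names only the visit made 2 to 3 days after the initial one. For that visit it reads: "visit record after the episode end date AND the record indicates site-observed symptom(s), adjust the episode end date to coincide with on-site visit date".

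The dates decide whether a case counts. SAP 4.2.1 requires the data for all three primary criteria to lie "within the start and stop dates of a continuous illness episode". SAP 4.2.2 does the same for the secondary endpoints, and the RSV episode definition in SAP 10.1 requires the swab to fall in that interval.

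The protocol produces the same observations at other visits. Section 6.2.3 allows the initial visit up to 7 days after onset. Section 6.2.4 encourages parents to report worsening, "which may trigger any number of additional follow-up visits at the" investigator's discretion.

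Some provisions bring findings back in. Under SAP 16.6 a hospital stay is itself an episode and is merged with an outpatient episode that overlaps or adjoins it. SAP 16.7 adds: "Two consecutive illness episodes that are within 7 days of each other will be combined as one continuous episode for the efficacy analysis". Finally, SAP 16.6 states: "Additional imputations may be performed by a Novavax medical staff if warranted in a blinded fashion".

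**The concern.** A parent's recalled date can take precedence over what trained staff saw, measured and swabbed. Whether it does depends on the label of the visit, not on what was found. An infant with an RSV-positive swab and qualifying tachypnea or hypoxemia could be analysed as a non-case for the primary endpoint.

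The narrow rule also sits badly with two other parts of the plan. It is stricter than the SAP's own rule for a missing date, and no reason is given. Protocol 6.2.5 says a new illness begins only after 7 days free of respiratory symptoms; an infant whom staff find symptomatic two days after the parent's date has not been symptom-free.

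At stake are some primary events, hence some power, and the reproducibility of the case count, because the last resort is a discretionary imputation.

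**Working it through.** **Step 1: one infant under each rule.** Take onset as day 0, a parent's return date of day 4, and an initial visit on day 6 with cough, qualifying tachypnea and an RSV-positive swab. A follow-up on day 8 or 9 finds no symptoms. There is no hospital stay and no second recorded episode.

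- Return date recorded: the episode runs from day 0 to day 4. The day 6 visit is not the 2–3 day visit, so the end date stays and all three elements fall outside.
- Return date missing, with day 6 the later of the last symptomatic parent contact and last symptomatic site visit: the end date becomes day 6 and all three elements fall inside.

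The clinical findings are identical; only the presence of the parent's date differs.

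**Step 2: routes by which such a finding can still count.**

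1. The 2–3 day visit records symptoms. The end date moves to that visit, which also takes in the earlier initial visit and its swab.
2. A second recorded episode starts within 6 days and is merged.
3. The illness overlaps or adjoins a hospital stay and is merged with it.
4. Sponsor medical staff make a blinded imputation.

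Routes 1 to 3 need a further recorded event. Route 4 has no stated criteria. Adjudication (SAP 10.2) judges whether the criteria are met in a plausible time sequence; it is given no stated power to move episode dates. The sensitivity analyses in SAP 16.8 address missing specimens and visits. These data are present but outside the dates, and that section does not name them.

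**Step 3: reproduce the stated power.** Inputs from SAP 13: 2,786 vaccine and 1,432 placebo infants, placebo risk 0.04, efficacy 65% (vaccine risk 0.35 × 0.04 = 0.014), null relative risk 0.70, one-sided alpha 0.0124.

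- Expected cases: 2,786 × 0.014 = 39.0 and 1,432 × 0.04 = 57.3, about 96 in all.
- SE of log RR = √[(1 − 0.014)/39.0 + (1 − 0.04)/57.3] = 0.205.
- Power = Φ[(ln 0.70 − ln 0.35)/SE − z(0.9876)] = Φ(0.693/0.205 − 2.24) = 87.2%, against 87% stated.

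An unpooled risk-difference version gives 85.2%, also within 2 points.

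**Step 4: size the loss.** The documents give no frequency, so the share lost is an assumption. It is taken as equal in both arms, which leaves the relative risk unchanged. Both risks are multiplied by (1 − share).

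| Share of cases lost (assumed) | Cases lost, of about 96 | Power, 4% placebo risk | Power, 3% placebo risk |
|---|---|---|---|
| 0% | 0 | 87.2% | 75.0% |
| 2% | 2 | 86.5% | 74.0% |
| 5% | 5 | 85.3% | 72.5% |
| 10% | 10 | 83.1% | 69.9% |

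**The case against.** The strongest reply is that little falls through. Protocol 6.2.4 schedules a 2–3 day follow-up for every symptomatic infant, and any symptom seen then recovers the initial visit as well. Discretionary later visits normally follow a parent's report of new or worse symptoms; those symptoms either lie inside the parent-reported episode or start a new one that merges if it is close enough. The 2–3 day label also ties the visit to the same illness, so the restriction has a purpose: an extension without a time limit could join a swab from one illness to tachypnea from another. And a 5% loss moves power by about as much as the choice between two normal approximations does (87.2% and 85.2%).

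Much of this stands. A reader might infer that findings after the parent's date can never form a case; the four routes in the working show otherwise. A reader might also infer that in-hospital visits are missed; they are not, because the stay is an episode in its own right.

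What remains is the lone qualifying outpatient visit: after the parent's date, with no symptomatic 2–3 day visit and nothing to merge with. Under the explicit rules it is excluded, and only an imputation without criteria can restore it. The follow-up route may also be weaker for earlier seasons, since the change history for protocol version 9.0 describes strengthening that visit.

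**Conclusion.** The gap is real and limited. When a return date is recorded, no pre-specified rule extends the episode for symptoms observed at an initial or a later discretionary outpatient visit. Inclusion then depends on a symptomatic 2–3 day visit, a merge, or unspecified blinded imputation. This is a stated rule that excludes some qualifying findings, not just a missing detail.

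The effect on power is probably modest: from about 87% to between 86.5% and 83% at 4% placebo risk and 65% efficacy, if 2% to 10% of cases are lost. That range rests on an assumed frequency and on equal loss in both arms. A reader might infer a biased efficacy estimate; the documents do not support that, since the dates are set blind and nothing points to differential loss. The case for changing the rule is that it decides primary cases, conflicts with the SAP's missing-date rule and the protocol's definition of a new illness, and is cheap to repair.

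**What to change.** Before unblinding, replace the extension rule in SAP 16.6 with:

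*If any on-site RSV surveillance visit (initial, 2–3 day or discretionary) for the same illness, occurring fewer than 7 days after the parent-reported return-to-normal date, records site-observed respiratory symptoms, the episode end date is moved to that visit date.*

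The 7-day limit and the same-illness condition prevent separate illnesses from being joined. Leave the 7-day separation rule, the hospital merges and adjudication as they are. Because the present 2–3 day provision has no time limit, count in the blinded run any such visit made 7 or more days after the parent's date, and state how it is handled.

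The cost is one sentence and a blinded re-run of the episode derivation on data already collected, with adjudication of any added potential cases. If unblinding has already happened, report the out-of-episode findings by arm and add an analysis that includes them, labelled post hoc.
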